	Grade 2 or 3	
 • Withhold study treatment. • Investigate etiology. Consult with a gastroenterologist if immune etiology is suspected. • Treat immune diarrhea/colitis with corticosteroids following guidance provided in the Appendix 10. • If diarrhea improves to Grade ≤ 1, resume obinutuzumab at full dose and resume lenalidomide at a reduced dose ^a per guidelines in Section 5.1.5. In case of immune-mediated event, atezolizumab may be resumed at full dose if colitis has cleared as confirmed by sigmoidoscopy (or colonoscopy, if appropriate) with colonic biopsy. Discuss with Medical Monitor before resuming atezolizumab. 
Note: If colitis is treated with corticosteroids, atezolizumab should not be resumed until the corticosteroids have been tapered to ≤ 10 mg/day of prednisone or equivalent (refer to Appendix 10 for guidance).

Table 11 Guidelines for Management of Non-Hematologic Toxicities (cont.)

Event		Action to Be Taken
Pneumopathy, non-infectious (i.e., dyspnea, hypoxia, pulmonary infiltrates)	Grade 3 or 4	
 • Permanently discontinue atezolizumab. Withhold obinutuzumab and lenalidomide. • Investigate etiology. Consult with a pulmonologist if immune etiology is suspected (refer to Appendix 10 for guidance). • Treat immune-mediated pneumopathy with corticosteroids following guidance provided in the Appendix 10. • If symptoms have resolved and CT lung findings are clear, resume obinutuzumab at full dose and resume lenalidomide at current dose.
	Grade 2	
 • Withhold atezolizumab for immune-mediated pneumopathy. • Treat with corticosteroids following guidance provided in the Appendix 10. • If there is improvement to Grade ≤ 1, resume atezolizumab after corticosteroids have been tapered (refer to Appendix 10 for guidance). Discuss with Medical Monitor before resuming atezolizumab. • Treat as Grade 3–4 if recurrent episode of immune pneumopathy.
Tumor flare reaction	Grade 3–4 ^c	
 • Withhold study treatment. • Administer corticosteroids, NSAIDs, and/or narcotic analgesics at investigator's discretion. • If there is improvement to Grade ≤ 1, resume obinutuzumab and atezolizumab at full dose and resume lenalidomide at a reduced dose per guidelines in Section 5.1.5 for current and subsequent cycles.

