Risks Associated with Atezolizumab and Guidelines for Management of Adverse Events Associated with Atezolizumab (cont.)

Table 2 Management Guidelines for Hepatic Events (cont.)

Event	Management
Hepatic event, Grade 3 or 4	
 • Permanently discontinue atezolizumab and contact Medical Monitor. ^c • Consider patient referral to gastrointestinal specialist for evaluation and liver biopsy to establish etiology of hepatic injury. • Initiate treatment with corticosteroids equivalent to 1–2 mg/kg/day oral prednisone. • If event does not improve within 48 hours after initiating corticosteroids, consider adding an immunosuppressive agent. • If event resolves to Grade 1 or better, taper corticosteroids over ≥1 month.

LFT = liver function test.

^a Atezolizumab may be withheld for a longer period of time (i.e., >12 weeks after event onset) to allow for corticosteroids (if initiated) to be reduced to the equivalent of ≤10 mg/day oral prednisone. The acceptable length of the extended period of time must be agreed upon by the investigator and the Medical Monitor.

^b If corticosteroids have been initiated, they must be tapered over ≥1 month to the equivalent of ≤10 mg/day oral prednisone before atezolizumab can be resumed.

^c Resumption of atezolizumab may be considered in patients who are deriving benefit and have fully recovered from the immune-mediated event. Patients can be re-challenged with atezolizumab only after approval has been documented by both the investigator (or an appropriate delegate) and the Medical Monitor.

GASTROINTESTINAL EVENTS

Immune-mediated colitis has been associated with the administration of atezolizumab. Management guidelines for diarrhea or colitis are provided in [Table 3](#).

All events of diarrhea or colitis should be thoroughly evaluated for other more common etiologies. For events of significant duration or magnitude or associated with signs of systemic inflammation or acute-phase reactants (e.g., increased C-reactive protein, platelet count, or bandemia): Perform sigmoidoscopy (or colonoscopy, if appropriate) with colonic biopsy, with three to five specimens for standard paraffin block to check for inflammation and lymphocytic infiltrates to confirm colitis diagnosis.

Appendix 10
Risks Associated with Atezolizumab and Guidelines for
Management of Adverse Events Associated with Atezolizumab
(cont.)

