Table 3 Management Guidelines for Gastrointestinal Events (Diarrhea or Colitis)

Event	Management
Diarrhea or colitis, Grade 1	
 • Continue atezolizumab. • Initiate symptomatic treatment. • Endoscopy is recommended if symptoms persist for >7 days. • Monitor closely.
Diarrhea or colitis, Grade 2	
 • Withhold atezolizumab for up to 12 weeks after event onset.^a • Initiate symptomatic treatment. • Patient referral to GI specialist is recommended. • For recurrent events or events that persist >5 days, initiate treatment with corticosteroids equivalent to 1–2 mg/kg/day oral prednisone. • If event resolves to Grade 1 or better, resume atezolizumab.^b • If event does not resolve to Grade 1 or better while withholding atezolizumab, permanently discontinue atezolizumab and contact Medical Monitor.^c
Diarrhea or colitis, Grade 3	
 • Withhold atezolizumab for up to 12 weeks after event onset.^a • Refer patient to GI specialist for evaluation and confirmatory biopsy. • Initiate treatment with corticosteroids equivalent to 1–2 mg/kg/day IV methylprednisolone and convert to 1–2 mg/kg/day oral prednisone or equivalent upon improvement. • If event resolves to Grade 1 or better, resume atezolizumab.^b • If event does not resolve to Grade 1 or better while withholding atezolizumab, permanently discontinue atezolizumab and contact Medical Monitor.^c

GI =gastrointestinal.

^a Atezolizumab may be withheld for a longer period of time (i.e., >12 weeks after event onset) to allow for corticosteroids (if initiated) to be reduced to the equivalent of ≤10 mg/day oral prednisone. The acceptable length of the extended period of time must be agreed upon by the investigator and the Medical Monitor.

^b If corticosteroids have been initiated, they must be tapered over ≥1 month to the equivalent of ≤10 mg/day oral prednisone before atezolizumab can be resumed.

^c Resumption of atezolizumab may be considered in patients who are deriving benefit and have fully recovered from the immune-mediated event. Patients can be re-challenged with atezolizumab only after approval has been documented by both the investigator (or an appropriate delegate) and the Medical Monitor.

Appendix 10

Risks Associated with Atezolizumab and Guidelines for Management of Adverse Events Associated with Atezolizumab (cont.)

Table 3 Management Guidelines for Gastrointestinal Events (Diarrhea or Colitis) (cont.)

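### Appendix 10 lets atezolizumab resume after Grade 2 or 3 immune colitis without the endoscopic clearance and Medical Monitor discussion that Table 11 requires, and no text says which table governs

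*Combined protocol and SAP*

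**What the plan says.** Table 11 in Section 5.1.5.1 has one row for Grade 2 or 3 diarrhea/colitis. Once the diarrhea is Grade 1 or better, obinutuzumab and lenalidomide may restart. For an immune-mediated event, atezolizumab carries extra conditions: "atezolizumab may be resumed at full dose if colitis has cleared as confirmed by sigmoidoscopy (or colonoscopy, if appropriate) with colonic biopsy", and "Discuss with Medical Monitor before resuming atezolizumab". A note adds: "If colitis is treated with corticosteroids, atezolizumab should not be resumed until the corticosteroids have been tapered to" 10 mg/day of prednisone or less. The row refers to Appendix 10 for steroid treatment ("Treat immune diarrhea/colitis with corticosteroids following guidance provided in the Appendix 10") and, in the note, for the taper.

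Appendix 10 Table 3 has separate Grade 2 and Grade 3 rows for diarrhea or colitis. Both give the same instruction: "If event resolves to Grade 1 or better, resume atezolizumab". The only condition attached is footnote b: "If corticosteroids have been initiated, they must be tapered over" at least one month, to 10 mg/day or less, before restarting. At Grade 2 the steroids themselves are conditional: "For recurrent events or events that persist >5 days, initiate treatment with corticosteroids".

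For Grade 2 hepatic events, Table 11 requires contact with the Medical Monitor before atezolizumab restarts. The Grade 2 row of Appendix 10 Table 2 says to resume at Grade 1 or better, with the same taper footnote and no such contact.

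**The concern.** The same patient falls under two resumption rules in one protocol, and the appendix rule is looser. Endoscopic and biopsy clearance is there because symptoms can settle before the mucosa does. The Medical Monitor discussion brings in a second judgment before re-exposure. A site that follows Appendix 10 Table 3 as written would restart atezolizumab on symptom grade and, where steroids were used, taper alone. What is at stake is patient safety and consistent conduct across about 15 sites, not the estimation of complete response.

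**Working it through.** This is a comparison of text, followed by a short calculation of how many patients it could touch.

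**1. Conditions for restarting atezolizumab after Grade 2 or 3 immune colitis**

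| Condition | Table 11 | Appendix 10 Table 3 |
|---|---|---|
| Event at Grade 1 or better | Yes | Yes |
| Clearance shown by endoscopy with biopsy | Yes | Not stated |
| Medical Monitor discussion before restart | Yes | Not stated |
| Steroids at 10 mg/day or less, if used | Yes | Yes, after a taper of at least one month |

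**2. Does Appendix 10 supply the missing conditions elsewhere?** No. The endoscopy in its gastrointestinal text is diagnostic, done to "check for inflammation and lymphocytic infiltrates to confirm colitis diagnosis". The biopsy in the Grade 3 row is likewise part of the initial evaluation. The Medical Monitor appears in the table for holds beyond 12 weeks (footnote a), for permanent discontinuation, and for re-challenge after it (footnote c). None of these covers an ordinary restart.

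**3. Does the 42-day rule close the gap?** Section 4.6.2 requires Medical Monitor approval once an immune-mediated event has kept atezolizumab on hold for more than 42 days. Assume the taper begins when the event improves and lasts the minimum month, 28 to 31 days. Then 42 − 28 = 14 and 42 − 31 = 11, so an event that improves within 11 to 14 days never reaches the rule. A first Grade 2 event that settles within 5 days starts no steroids under Appendix 10, so the taper condition does not apply either.

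**4. Grade 2 hepatic events.** Set side by side, Table 11 asks for Medical Monitor contact before restart and Appendix 10 Table 2 does not.

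**5. How many patients?** Inputs:
- Planned enrollment of 46 (Section 3.1.1).
- Grade 2 immune colitis in 0.4% (Section 5.1.4, Table 8, footnote f).
- Atezolizumab-related serious colitis in 0.5% (Section 1.3.2.1).

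Expected events are 46 × 0.004 = 0.18 and 46 × 0.005 = 0.23. The chance of at least one is 1 − 0.996^46 = 0.17 and 1 − 0.995^46 = 0.21. The documents give no rate for Grade 2 hepatic events, so no count is offered for them.

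**The case against.** The best defense is that the protocol as a whole points to Table 11. Section 1.3.2.1 places management of immune-mediated events in Section 5.1.5. Section 5.1 does the same for delays and discontinuation. Sections 4.3.2.2 and 4.6.2 refer to Section 5.1, and Table 12 sends maintenance patients to Table 11. The two rules are also compatible, since a site that applies the stricter one meets both. And colitis and hepatitis are adverse events of special interest (Section 5.2.3), reportable within 24 hours, with recovery reportable on the same clock (Section 5.4), so the sponsor should know about the case.

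Most of this stands, and it narrows the point. It does not remove it. Reporting a recovery is neither a discussion before restart nor evidence of mucosal clearance. The introduction to Table 11 itself sends readers to Appendix 10 for detailed management of atezolizumab events, and no sentence ranks the two.

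A reader might infer that Table 11 steers sites to the looser rule. It does not. The colitis row hands over only steroid treatment and taper, and both safeguards appear just before the note that cites Appendix 10. Only someone using Appendix 10 alone is misled.

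A reader might also see conflicts in the Grade 2 hepatic steroid condition and duration trigger. These largely disappear in context. The Appendix 10 hepatic text is about immune-mediated hepatitis and asks that drug, viral, toxic and neoplastic causes be considered. Footnote c, attached to that row, speaks of an immune-mediated event. The two duration triggers overlap. For Grade 3 or 4 hepatic events the tables agree when the event is immune-mediated, and the appendix context implies that it is, so no wrong action follows.

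**Conclusion.** The inconsistency is real and concerns safety management. Appendix 10 Table 3 omits two conditions that Table 11 sets for restarting atezolizumab after Grade 2 or 3 immune colitis. Appendix 10 Table 2 omits one that Table 11 sets after Grade 2 hepatic events. No text says which table governs.

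The size is small: about 0.2 immune colitis events among 46 patients. This assumes single-agent atezolizumab rates carry over, because the documents give none for the triplet. The 0.5% figure is not split by grade and may include Grade 4 cases, which both tables take off atezolizumab. The count is of events; restarts made under Appendix 10 alone would be fewer.

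A reader might reach for a larger number from the 8% rate of Grade 3–4 treatment-related diarrhea with atezolizumab plus obinutuzumab (Section 1.4.3.2). That rate is not specific to immune-mediated events, and the endoscopic condition applies only to those. Nor do the documents support any effect on the primary endpoint or on another analysis.

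**What to change.** - In Appendix 10 Table 3, Grade 2 and Grade 3 rows, add Table 11's endoscopy and biopsy clearance and Medical Monitor discussion for immune-mediated events. Alternatively, replace the resume lines with a reference to Table 11, as Appendix 10 already does for endocrine events.
- In the Grade 2 row of Appendix 10 Table 2, add Medical Monitor contact before atezolizumab restarts.
- State once, in Section 5.1.5.1 and in Appendix 10, that Table 11 governs withholding and resumption where the two differ.

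The cost is amendment wording. No procedure, visit or data item is added, because Table 11 already requires these steps.

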	Grade 1–2 ^c	
 • Continue study treatment. • Administer corticosteroids, NSAIDs, and/or narcotic analgesics at investigator's discretion.

Table 11 Guidelines for Management of Non-Hematologic Toxicities (cont.)

Event		Action to Be Taken
Dermatologic toxicity: Grade ≥ 2	Grade 3 with blistering or Grade 4	
 Permanently discontinue study treatment.
	Grade 2 or Grade 3 without blistering	
First occurrence:
 
 Withhold study treatment and evaluate patient at least every 7 days. Investigate etiology. Consult with a dermatologist. Topical corticosteroids may be required. If immune etiology is suspected, consider oral prednisone 10 mg or equivalent. If event is unresolved after 48–72 hours, administer oral prednisone 60 mg or equivalent. If there is improvement to Grade ≤ 1, resume obinutuzumab at full dose and resume lenalidomide at a reduced dose^a per guidelines in Section 5.1.5 for current and subsequent cycles. Atezolizumab may be resumed at full dose if the event is resolved and systemic corticosteroids dose is ≤ 10 mg/day of oral prednisone or equivalent. Contact Medical Monitor before resuming atezolizumab. 
Second occurrence:
 
 Permanently discontinue study treatment.
Hypothyroidism		
 Investigate etiology. Consult with an endocrinologist (refer to the Appendix 10 for guidance if immune etiology is suspected). Start thyroid replacement hormone. Monitor TSH weekly. 
Asymptomatic elevation of TSH
 
 Continue study treatment. 
Symptomatic elevation of TSH
 
 Withhold study treatment. If symptoms are controlled and TSH levels are decreasing, resume obinutuzumab and atezolizumab at full dose and lenalidomide at current dose. Permanently discontinue atezolizumab for Grade ≥ 3 hypothyroidism.

Table 11 Guidelines for Management of Non-Hematologic Toxicities (cont.)

Event	Action to Be Taken

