Hyperthyroidism (cont.)	
For asymptomatic patients with TSH < 0.5 mU/L:
 
 • Perform TSH, free T4, and T3 tests every 4 weeks. 
For asymptomatic patients with TSH < 0.1 mU/L or symptomatic patients:
 
 • Withhold study treatment. • Consider consultation with an endocrinologist. • Administer methimazole as needed. • Resume atezolizumab when symptoms are controlled by thyroid hormone replacement. • Permanently discontinue atezolizumab for life-threatening hyperthyroidism.
Hypophysitis (pan-hypopituitarism)	Grade 4 
 • Permanently discontinue atezolizumab and contact Medical Monitor. • Refer patient to endocrinologist. • Perform brain MRI (pituitary protocol). • Initiate treatment with 1–2 mg/kg/day IV methylprednisolone or equivalent and convert to 1–2 mg/kg/day oral prednisone or equivalent upon improvement. • Initiate hormone replacement if clinically indicated.
	Grade 2 or 3 
 • Withhold atezolizumab. • Refer patient to endocrinologist. • Perform brain MRI (pituitary protocol). • Initiate treatment with 1–2 mg/kg/day IV methylprednisolone or equivalent and convert to 1–2 mg/kg/day oral prednisone or equivalent upon improvement. • Initiate hormone replacement if clinically indicated. • Resume atezolizumab if event resolves to Grade 1 or better, and patient is stable on replacement therapy (if required) within 12 weeks. • If event does not resolve to Grade 1 or better while withholding atezolizumab, permanently discontinue atezolizumab and contact Medical Monitor. • For recurrent hypophysitis, treat as a Grade 4 event.

Table 11 Guidelines for Management of Non-Hematologic Toxicities (cont.)

Event		Action to Be Taken
Hyperglycemia	Grade 3–4	
 • Withhold atezolizumab. • Initiate treatment with insulin. • Monitor for glucose control. • Resume atezolizumab when symptoms resolve and glucose levels are stable.
	Grade 1 or 2	
 • Continue atezolizumab. • Investigate for diabetes. If patient has Type 1 diabetes, treat as a Grade 3 event. If patient does not have Type 1 diabetes, treat as per institutional guidelines. • Monitor for glucose control.

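### Table 11's hyperthyroidism row treats with methimazole but restarts atezolizumab on thyroid hormone replacement, the hypothyroidism treatment (minor wording error)

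*Combined protocol and SAP*

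**What the plan says.** Table 11 in Section 5.1.5.1 has one row for hyperthyroidism, marked as a continuation, with two subgroups.

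- **Tested, not held.** Under "For asymptomatic patients with TSH < 0.5 mU/L", the action is "Perform TSH, free T4, and T3 tests every 4 weeks".
- **Held.** Under "For asymptomatic patients with TSH < 0.1 mU/L or symptomatic patients", study treatment is withheld, an endocrinology consultation is to be considered, and the drug instruction is "Administer methimazole as needed". The next line is "Resume atezolizumab when symptoms are controlled by thyroid hormone replacement". Life-threatening cases stop atezolizumab permanently.

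The hypothyroidism row directly above says "Start thyroid replacement hormone" and "Monitor TSH weekly". When study treatment has been withheld for symptomatic TSH elevation, its restart condition begins "If symptoms are controlled and TSH levels are decreasing" and then names all three drugs with their doses.

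Section 2 defines study treatment as all components together, so the hyperthyroidism hold covers obinutuzumab and lenalidomide as well as atezolizumab.

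**The concern.** The row gives an antithyroid drug and then makes restart depend on thyroid hormone replacement, which treats the opposite condition. It reads as a phrase carried over from the hypothyroidism row, although the documents do not say how it arose.

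Hyperthyroidism is a foreseeable event here. Section 5.2.3 lists it among the atezolizumab adverse events of special interest, and Section 5.1.3.9 says it has been reported with lenalidomide. A site following the line literally would either keep atezolizumab on hold or have to query the Medical Monitor.

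Hold time counts. Under Section 4.6.2 and the Table 11 general guidance, an immune-mediated event that keeps atezolizumab on hold for more than 42 days leads to permanent discontinuation unless the Medical Monitor approves otherwise. For a treatment-related event judged not immune-mediated, the limit is 21 days. The opposite risk also exists: a patient held on TSH alone could restart at once, because there are no symptoms to control.

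**Working it through.** No sample size, error rate or estimate is involved, so the check is textual.

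**Step 1. Apply the restart line to each kind of held patient.**

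| Held patient | Treatment the row provides | Restart line as worded |
|---|---|---|
| Symptomatic, controlled on methimazole | Methimazole | Not met: control did not come from hormone replacement |
| Asymptomatic, TSH below 0.1 mU/L | Methimazole as needed | Met at once (no symptoms) or undefined (no replacement given) |
| Symptomatic, later hypothyroid and on replacement | None stated in this row | Could be met, but the row does not describe this patient |

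The line works only for the third patient, whom the row does not mention.

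**Step 2. Look for another restart rule in induction.**

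- Appendix 10, Endocrine Events, sends the reader back to Table 11 and adds diagnostic advice only.
- The last row of Table 11, for other non-hematologic toxicities, covers only events not described earlier in the table. Hyperthyroidism is described.
- The general guidance at the head of Table 11 sets maximum delays. A maximum delay says when to stop treatment for good, not when to resume it.
- Section 5.1.5 gives recovery rules for lenalidomide-related toxicity, but they govern lenalidomide dosing and not atezolizumab.

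None of these fills the gap.

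**Step 3. Compare with neighbouring rows.** Hypothyroidism uses symptom control plus the direction of TSH. Hyperglycemia (Grade 3–4) uses symptom resolution plus stable glucose. Both pair a clinical criterion with a laboratory one suited to the event. The hyperthyroidism row has no laboratory criterion and names the wrong therapy.

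**Step 4. Check which drugs are covered.** The hold applies to all three drugs, but the restart line names atezolizumab alone. The general guidance partly covers the other two: drugs are normally held and resumed together, and obinutuzumab and lenalidomide may go ahead alone if an atezolizumab delay over 21 days is expected and nothing contraindicates it.

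**Step 5. Check maintenance.** Table 12 (Section 5.1.5.2) sends atezolizumab-related toxicities of possible immune origin to Table 11, but its bracketed list names hypothyroidism and not hyperthyroidism. Myocarditis and nephritis are also absent, so the list may not be complete. If hyperthyroidism is outside the list, Table 12's own rule for events of Grade 2 or higher applies (improvement to Grade 1 or lower, or baseline), and that rule is usable. Maintenance is therefore unclear, but not shown to be wrong.

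**Step 6. Size.** The documents give no hyperthyroidism rate. With about 46 patients planned, each percentage point of incidence is 46 × 0.01 = 0.46 of a patient. That figure covers the whole study and includes patients who would never be held.

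**The case against.** The best defence is that no competent site would be misled. Section 5.1.5.1 says atezolizumab toxicities are managed by standard medical practice, the row points to an endocrinologist, the Medical Monitor can approve a hold beyond 42 days, and Appendix 10 allows approved re-challenge even after permanent discontinuation. This stands, and it is why the point is minor. It does not make the line right. It asks sites to read past a written dosing rule, and Section 9.2 requires deviations to be documented and bars prospective requests to deviate.

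A second defence is that replacement fits patients who become hypothyroid after the hyperthyroid phase. That is possible, but the row does not say so, and the other two kinds of held patient would still have no rule.

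A third is that the row is a continuation whose first part is not in the available text. The hold, the methimazole instruction and the restart line run together under one subgroup heading, so their conflict does not depend on the missing part. The caution does apply to anything claimed to be absent from the row.

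For that reason one stronger reading should be resisted. A reader might infer that symptomatic patients go unmonitored, since the 4-weekly tests are written under the asymptomatic subgroup and Appendix 1 schedules thyroid tests every 3 months. The documents do not support this. The unseen part of the row may contain monitoring instructions, Section 5.5.1 has investigators follow every adverse event until it resolves or is stable, and Section 5.1.3.9 recommends ongoing thyroid monitoring.

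**Conclusion.** The point holds as a wording error in an operative dosing rule: the restart line in the hyperthyroidism row is wrong as written for induction, and no other visible text replaces it.

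Its size is small. It affects only patients held for hyperthyroidism, probably few, although the documents give no rate from which to count them. The likely cost is an avoidable delay or a Medical Monitor query. Loss of atezolizumab would need a hold beyond the applicable limit and, for an immune-mediated event, no Medical Monitor approval.

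A reader might go further and infer a threat to the trial's results. The documents do not support that: the primary analysis, the sample size and the safety stopping rules do not use this row. The conclusion assumes that the unseen first part of the row does not contain a separate restart rule.

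**What to change.** Replace the restart line with wording to this effect: *once symptoms, if any, are controlled and thyroid function (TSH, free T4, T3) is improving, restart all three drugs, with obinutuzumab and atezolizumab at full dose and lenalidomide at its current dose; repeat thyroid tests as clinically needed to support the decision.* This follows the form of the hypothyroidism row, covers patients held on TSH alone, and supplies the missing rule for the other two drugs.

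Do not tie restart to a fixed 4-weekly test. The first such test would fall on day 28, beyond the 21-day mark in the general guidance, and could itself delay a patient who had already recovered.

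If Table 11 is meant to govern hyperthyroidism in maintenance, add the event to the bracketed list in Table 12.

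The cost is one sentence in Table 11 and, if wanted, one word in Table 12, at the next amendment. No scheduled visits or tests are added, and no analysis changes.
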